## 11.2 Statistical Analyses

Individual and mean concentration of hormonal levels versus nominal time curves will be presented by treatment group for each evaluation timepoint. Descriptive statistics (sample size “n”, mean, standard deviation, coefficient of variation, median, minimum value and maximum value) of hormonal levels will be presented for each timepoint.

Summaries of the LH, FSH,  $E_2$ , and progesterone levels will be reported for each dosing and post-dosing evaluation timepoint, for the dosing days 22 and 28 (Day 29 for Treatments “C” and “D”) (combined: i.e. the maximum among the 2 values) and, optionally, for the entire 28-day dosing period and the entire post-dosing Evaluation Period. Changes from pre-dosing baseline in LH, FSH,  $E_2$  and progesterone levels will also be summarized (sample size “n”, mean, standard deviation, median, minimum value and maximum value) at each on-treatment evaluation timepoint. Pre-dosing baseline for all PD metrics is the highest value across two observations: (a) screening measurement and (b) measurement taken just prior to the first dose of the study drug. Similar summaries will be provided for the follow-up visits (postdosing Days 7, 14, 21, and 28). In addition, time to return to pre-study baseline hormonal levels could be estimated.

Summaries of PD metrics may be further stratified by the cycle period (days) of the start of dosing. Categorical variables will be summarized by using frequency counts and percentages for each treatment by visits involved. In addition, the number of patients with missing values will be displayed.

Additionally, correlations between leuprolide concentration levels and PD parameters will be examined graphically. PD parameters may include LS, FSH, E2 and progesterone levels. These evaluations will not be performed for Treatment “D”.

Number of vaginal (menstrual) bleeding days will be summarized by treatment group for 28 days of therapy and for 28 days of post-study follow-up. The subject incidence of the onset of menstrual period after completion of therapy will be reported for each treatment group.

The onset of menstrual period is defined as at least three consecutive bleeding/spotting days during the 28-day postdosing period.

Additional PD analyses could be performed if necessary.

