empty stomach. Note: On an empty stomach means that the oral doses are administered at least 2 hours before and at least 2 hours after the meal. For clarity, all oral doses have to be taken on an empty stomach except for the morning doses of Days 1 and 28, for which the fasting period is -10h to +4h. Subjects randomized to the two oral doses (Treatments “A” and “B”) will have twenty-four (24) serial serum samples drawn on Treatment Days 1 and 28 immediately prior to dosing (0 time), and at 0.5, 1, 1.5, 2, 2.5, 3, 3.5, 4, 4.5, 5, 6, 7, 8, 10, 12, 13, 14, 15, 16, 17, 18, 20, and 24 hours following oral dosing. For Treatment “B”, the PK blood draws will be drawn for the morning dose. For the IM injection (Treatment “C”), serial serum samples will also be drawn on Treatment Day 1, prior to dosing (0 time), at 0.5, 1, 2, 6, 12, 18, and 24 hours postdosing. Blood samples for the IM injection will also be taken in the morning on Postdosing Day 1. Additional blood samples for all subjects will be taken in the morning (in the oral groups, just prior to dosing) on Treatment Days 8, 15, and 22. Samples will be appropriately stored until they can be assayed for leuprolide and hormonal levels. Serum concentrations of LH, FSH, E2, and progesterone will be measured (immediately prior to dosing) on Treatment Days 1, 8, 15, 22, and in the morning of Day 29.

Subjects enrolled to the third oral dose (Treatment “D”) will have a dosing initiation visit scheduled 5-9 days before the anticipated start of their next menstrual cycle, based on their self-reported menstrual cycle length and the day the current menstrual cycle began. During the visit, just prior to the first dosing, baseline blood samples will be taken for leuprolide and hormonal levels. The same blood draws will be performed immediately prior to the first dose of the day on Treatment Days 8, 15, 22, and in the morning of Day 29.

On Day 29, after the 24-hour blood draws in the oral groups (Treatments “A” and “B”) and after the PK/PD blood draws in the Treatment “D” and the IM injection group (Treatment “C”), physical, gynecological, and safety laboratory evaluations will be performed.

Note: throughout the text, Treatment Day 29 may be used interchangeably with Postdosing Day 1.

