After the 28-day dosing period, four follow-up visits will be scheduled at 7, 14, 21, and 28 days after the last dose. During each follow-up visit, blood samples will be drawn to assess leuprolide (via a single blood draw) and LH, FSH, E2, and progesterone concentrations. During each follow-up visit, subjects will be asked about onset (or absence) of menstrual period.

Safety laboratory evaluations will also be performed during the 28-day postdosing visit. The 28-day postdosing visit will be considered the Final Study Visit. In addition to the PK/PD and safety laboratory assessments, ECG, physical and gynecological examinations will also be performed.

A total of 55 PK blood samples will be taken from subjects in the oral groups (Treatments “A”, and “B”) for the evaluation of the leuprolide serum concentrations. A total of 11 PD blood samples will also be taken for the determination of LH, FSH, E2, and progesterone levels. The blood volume for each PK sample is assumed to be approximately 3 mL for leuprolide analysis, and the volume for each PD sample is assumed to be approximately 16 mL (10 mL for progesterone and estradiol analysis, and 6 mL for FSH and LH analysis). The total amount of blood volume for all PK and PD draws is 341 mL. Four safety blood draws will be performed during the study with a volume of 8 mL per draw. An

additional 34 mL of blood may be drawn during the study to allow for repeat draws and/or additional safety tests and for the screening pregnancy test. The total amount of blood drawn should not exceed 407 mL over 3 months, including all samples collected for PK and PD analyses and eligibility and safety purposes.

In the Treatment group “D” the total number of samples for PK evaluations will be reduced by 46 when compared to other oral groups. The total amount of blood drawn will be reduced by 138 mL (46 x 3 mL) and should not exceed 269 mL over 3 months, including all samples collected for PK and PD analyses and eligibility and safety purposes.

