A total of 16 PK blood samples will be taken from subjects in the Lupron group (Treatment “C”) for the evaluation of the leuprolide serum concentrations. A total of 10 PD blood samples will also be taken for the determination of LH, FSH, E2, and progesterone levels. The total amount of blood volume for all PK and PD draws is 208 mL. Four safety blood draws will be performed during the study with a volume of 8 mL per draw. An additional 34 mL of blood may be drawn during the study to allow for repeat draws and/or additional safety tests and for the screening pregnancy test. The total amount of blood drawn in the Lupron group should not exceed 274 mL over 3 months, including all samples collected for PK and PD analyses and eligibility and safety purposes.

Serum concentrations of leuprolide and concentrations of PD parameters will be determined via validated bioanalytical methods. Sensitivity and specificity of the employed bioanalytical methods will be described in the study report.

A number of PK parameters will be evaluated for each subject for each evaluation period (*ie*, Treatment Days 1 and 28 for the two oral groups (Treatments “A” and “B”) and day 1 for the Lupron Depot group (*eg*, Cmax, Tmax, AUC0-24, AUC0-t, Css, etc). PD parameters will include values of the hormones measured (LH, FSH, E2, and progesterone) in relation to the baseline values and/or prespecified thresholds). See Section 12.2 and Section 12.3 for the detailed description of the PK and PD parameters and planned statistical analyses.

During both the 28-day dosing period and postdosing 28-day follow-up, subjects will record vaginal (menstrual) bleeding on diary cards. Clinically notable events (including possible flare-up symptoms) may also be recorded. See APPENDIX F for a sample diary card.

The evaluation of safety will be based on the incidence of TEAEs, discontinuations due to TEAEs, treatment-induced changes in vital signs, body weight, physical and gynecological examinations, and laboratory test results.

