### 12.3 Pharmacodynamic Parameters and Analyses

As noted earlier, PD assessments (LH, FSH, E2, and progesterone) will be performed during the Screening Visit and immediately prior to dosing on Treatment Days 1, 8, 15, 22, and 29. Additional PD assessments will be performed during the follow-up visits (postdosing Days 7, 14, 21 and 28).

The primary PD metric - suppression of E2 level - will be assessed at each on-treatment evaluation timepoint. Treatment Day 22 and Treatment Day 28 evaluations (separately and combined) will be considered as most important. The summaries will also be provided across the entire dosing period and the entire postdosing period, separately and combined. The summaries of PD metrics may be further stratified by the cycle period (days) of the start of dosing.

In addition to a primary E2 suppression threshold (E2 ≤40 pg/mL), a suppression of E2 below 20 pg/mL may also be assessed, if considered necessary. The suppression of ovulation (as evidenced by progesterone levels <3 ng/mL) will be evaluated with Treatment Day 22 and Postdosing Day 1 assessments positioned as primary. Changes from predosing baseline in E2 and progesterone levels will also be summarized at each on-treatment evaluation timepoint. Predosing baseline for all PD metrics is the highest value across two observations: (a) screening measurement and (b) measurement taken just prior to the first dose of the study drug. Similar summaries will be provided for the follow-up visits (postdosing Days 7, 14, 21, and 28). In addition, time to return to prestudy baseline hormonal levels could be estimated.

PD parameters will be graphed by treatment group for each evaluation period.

Additionally, correlations between leuprolide concentration levels and PD parameters will be examined.

Number of vaginal (menstrual) bleeding days will be summarized by treatment group for 28 days of therapy and for 28 days of poststudy follow-up. The subject incidence of the onset of menstrual period after completion of therapy will be reported for each treatment group.

Further details of the PD data analysis will be disclosed in the SAP.

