### **Endometriosis**

In controlled clinical studies, LUPRON DEPOT 3.75 mg monthly for six months was shown to be comparable to danazol 800 mg/day in relieving the clinical sign/symptoms of endometriosis (pelvic pain, dysmenorrhea, dyspareunia, pelvic tenderness, and induration) and in reducing the size of endometrial implants as evidenced by laparoscopy. The clinical significance of a decrease in endometriotic lesions is not known at this time, and in addition laparoscopic staging of endometriosis does not necessarily correlate with the severity of symptoms.

LUPRON DEPOT 3.75 mg monthly induced amenorrhea in 74% and 98% of the patients after the first and second treatment months respectively. Most of the remaining patients reported episodes of only light bleeding or spotting. In the first, second and third post-treatment months, normal menstrual cycles resumed in 7%, 71% and 95% of patients, respectively, excluding those who became pregnant.

Figure 1 illustrates the percent of patients with symptoms at baseline, final treatment visit and sustained relief at 6 and 12 months following discontinuation of treatment for the various symptoms evaluated during two controlled clinical studies. This included all patients at end of treatment and those who elected to participate in the follow-up period. This might provide a slight bias in the results at follow-up as 75% of the original patients entered the follow-up study, and 36% were evaluated at 6 months and 26% at 12 months.

**FIGURE 1—PERCENT OF PATIENTS WITH SIGN/SYMBOLS AT BASELINE, FINAL TREATMENT VISIT, AND AFTER 6 AND 12 MONTHS OF FOLLOW-UP**

[figure not shown]

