***PART 2: 28-Day Post-Dosing Evaluation Period***

Date (MM/DD)																												
Post-dosing Day →	1	2	3	4	5	6	7	8	9	10	11	12	13	14	15	16	17	18	19	20	21	22	23	24	25	26	27	28
Bleeding Diary																												
Check if NO BLEEDING/SPOTTING																												
Check if SPOTTING																												
Check if LIGHT bleeding																												
Check if NORMAL bleeding																												
Check if HEAVY bleeding																												

Principal Investigator or Designee Signature: \_\_\_\_\_ Date: \_\_\_\_\_

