**Table 3-1 Treatment Description**

Treatment	Description
A	Leuprolide Oral Tablet, Ovarest™ 4 mg, administered qd for 28 consecutive days
B	Leuprolide Oral Tablet, Ovarest™ 4 mg, administered bid for 28 consecutive days
C	Leuprolide Acetate IM, Lupron Depot® 3.75 mg, administered for one month of therapy
D	Leuprolide Oral Tablet, Ovarest™ 10 mg, administered bid for 28 consecutive days

Subjects meeting the eligibility criteria were to be initially randomized to receive one of the two doses of Ovarest™ for 28 days or a monthly IM dose of Lupron Depot®. After the protocol amendment, subjects meeting the eligibility criteria were to be enrolled in Treatment “D” The initially randomized subjects had to start dosing (Treatment Day 1) on either days 1-4 or days 18-28 of their menstrual cycle. Subjects enrolled to the third oral dose (Treatment “D”) had to start dosing 5-9 days before the anticipated start of their next menstrual cycle, based on their self-reported menstrual cycle length and the day the current menstrual cycle began.

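### SAP 11.2 does not require the bleeding run to begin after dosing, so a period that starts on treatment can be counted as menstrual onset after therapy

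*SAP*

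**What the plan says.** Protocol 12.3 sets the summary: "The subject incidence of the onset of menstrual period after completion of therapy will be reported for each treatment group". The protocol gives no working definition of onset. SAP 11.2 repeats the summary and supplies the only rule: "The onset of menstrual period is defined as at least three consecutive bleeding/spotting days during the 28-day postdosing period".

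The surrounding text fixes the window and the data available:

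- Protocol 7.1 places the boundary: "Treatment Day 29 may be used interchangeably with Postdosing Day 1". The postdosing period is therefore Treatment Days 29 to 56.
- Protocol 7.1 has bleeding recorded on both sides of it: "During both the 28-day dosing period and postdosing 28-day follow-up, subjects will record vaginal (menstrual) bleeding on diary cards".
- Part 2 of the diary card (Protocol Appendix F) has a separate row, "Check if SPOTTING", apart from the rows for light, normal and heavy bleeding.
- Protocol 7.1 adds a second source, which the SAP rule does not use: "During each follow-up visit, subjects will be asked about onset (or absence) of menstrual period".

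**The concern.** The summary is meant to describe menses returning after the drug is stopped. The rule only asks whether three consecutive days of bleeding or spotting fall inside the window. Three consequences follow from its wording.

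1. A period that began on Treatment Day 27 or 28 and is still running on postdosing Day 3 counts as post-therapy onset, although it shows bleeding on treatment.
2. Three days of spotting count as a period, because the rule treats bleeding and spotting alike.
3. A period that begins on postdosing Day 27 or 28 cannot count, because only two or one diary days remain.

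On-treatment periods are plausible in A and B: Protocol Section 5 reports that estradiol suppression with both 4 mg regimens was well below that with Lupron Depot. The start windows also allow the overlap. SAP 3.3 says that the initially randomized women "had to start dosing (Treatment Day 1) on either days 1-4 or days 18-28 of their menstrual cycle", so with a cycle of about four weeks an early starter who is not suppressed is next due close to Treatment Day 28. At stake is the reading of one descriptive summary in very small groups.

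**Working it through.** The plan gives no figure to reproduce, so the rule was applied literally to projected cycles.

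**Inputs from the documents.** Postdosing Days 1-28 are Treatment Days 29-56. Cycle length is 21 to 35 days (Protocol 8.1). A-C may start on cycle Days 1-4 or in the last 11 days of the cycle (Protocol Appendix G). D starts 5-9 days before the next expected period. Groups are 9, 9 and 5 women in A, B and C, and up to 12 in D (Protocol 7.1).

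**Assumptions.** Fixed cycle length, no suppression, and a bleed of L days. The documents give no bleed length, so L = 5 is used, with 3 to 7 as the range.

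**Which periods cross.** A period starting on Treatment Day s crosses and meets the rule if s ≤ 28 and s + L − 1 ≥ 31, that is, 32 − L ≤ s ≤ 28. For L = 5, s is 27 or 28. For L = 3, no start qualifies.

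**Projected periods.** In A-C, a woman with cycle length C who starts on cycle Day d is next due on Treatment Day C − d + 2, then every C days. With C = 28 and d = 1, 2, 3, 4 this gives Treatment Days 29, 28, 27, 26. In D, with the first dose b days before menses, periods fall on Treatment Days 1 + b, 1 + b + C, and so on.

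**When the crossing run decides the result.** The summary is yes or no per woman. If a later period starts on Treatment Days 29-54, three of its days fit in the window and she counts anyway. The crossing run decides only when no such period exists.

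**Counts.** A-C: 15 cycle lengths × (4 + 11) start days = 225 combinations. D: 15 × 5 = 75.

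| Bleed length (days) | A-C crossing | A-C decisive | D crossing | D decisive |
|---|---|---|---|---|
| 3 | 0 | 0 | 0 | 0 |
| 4 | 10 | 4 | 2 | 0 |
| 5 | 19 | 6 | 3 | 0 |
| 6 | 27 | 6 | 3 | 0 |
| 7 | 34 | 6 | 3 | 0 |

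For L = 5 this is 19/225 = 8.4% crossing and 6/225 = 2.7% decisive in A-C. The six decisive cases are below.

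| Cycle length | Start day | Crossing period starts (Treatment Day) | Next period starts (Treatment Day) |
|---|---|---|---|
| 27 | 1 | 28 | 55 |
| 28 | 2 | 28 | 56 |
| 28 | 3 | 27 | 55 |
| 29 | 3 | 28 | 57 |
| 29 | 4 | 27 | 56 |
| 30 | 4 | 28 | 58 |

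All six start on cycle Days 1-4, which both the protocol and the SAP allow. In four of them the next period starts on Treatment Day 55 or 56 (postdosing Day 27 or 28). If such truncated runs were counted as onset, only 2 of 225 would depend on the crossing run.

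**Weight of one woman.** 100/9 = 11.1 points in A or B; 100/5 = 20.0 in C; 100/12 = 8.3 in D.

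**Spotting.** A spotting-only run on postdosing Days 10-12 meets the rule. The documents give no basis for estimating how often this would occur.

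**The case against.** The strongest reply is that onset already means a new start, and that the definition directly follows a sentence about the time after therapy. That is probably the intent, but a programmer coding the definition would not enforce it. The Day 29 rule in SAP 11.1 does not help, because it assigns hormone measurements to the dosing interval and does not deal with bleeding runs.

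The second reply concerns size, and it stands. Most women whose bleeding crosses the boundary would have another period in the window and count either way. A reader might take the early starts alone (8 of 60, or 13%, for a 5-day bleed) as the share misclassified, or note that with a 21-day cycle two of the five start days in D give a crossing period. Neither is a misclassification rate. The first leaves out the late start days; the women in the second are next due on Treatment Days 48 and 49, well inside the window. The 20-point weight belongs to Lupron Depot, where unsuppressed menses are least expected given the suppression reported. The 8-point weight belongs to D, where no crossing run is decisive in this model.

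Third, a reader might call this the trial's measure of reversibility and infer that a poorly suppressed group would pass for one that recovers quickly. The documents do not support that. LH, FSH, estradiol and progesterone are also summarized on postdosing Days 7, 14, 21 and 28, bleeding days on therapy are reported separately, and estradiol suppression is shown by group. The summary is an incidence, not a speed of recovery.

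Finally, the appended label does not settle what intensity makes a period. Of women without amenorrhea on Lupron Depot, it says "Most of the remaining patients reported episodes of only light bleeding or spotting", which groups light bleeding with spotting. It supports showing spotting separately, not a particular cut-off.

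**Conclusion.** The definition does not match the quantity it is meant to report. As written it can count on-treatment bleeding as post-therapy onset, it counts spotting-only runs as menses, and it cannot register an onset in the last two diary days. The boundary effect is modest: a 5-day bleed gives 6 decisive combinations of 225 in A-C and none of 75 in D, and bleeds of 3 to 7 days give 0 to 6 and none. These counts weight all combinations equally and assume fixed cycles and no suppression, so they are not probabilities for subjects. The summary is descriptive and is not the primary estradiol endpoint. The rule is still worth correcting, because one woman moves the figure by about 11 points in A or B and the diary already holds what is needed.

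**What to change.** In SAP 11.2:

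- Define onset as the first day of a run of at least three consecutive bleeding or spotting days, where that first day is postdosing Day 1 or later. If it is Day 1, Treatment Day 28 must be recorded as free of bleeding and spotting.
- Report runs already in progress on Treatment Day 28 as on-treatment bleeding.
- Show runs made up only of spotting on a separate line.
- List runs that start on postdosing Day 27 or 28 and are cut off by the end of the diary as indeterminate, neither onset nor no onset.

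Under this rule, four of the six decisive cases above become indeterminate and two become no onset. The cost is SAP wording and slightly more derivation work, with no new data collection. A few women may move out of the onset count.

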
Subjects enrolled to the third oral dose (Treatment “D”) will have a dosing

initiation visit scheduled 5-9 days before the anticipated start of their next menstrual cycle, based on their self-reported menstrual cycle length and the day the current menstrual cycle began. During the visit, just prior to the first dosing, baseline blood samples will be taken for leuprolide and hormonal levels. The same blood draws will be performed immediately prior to the first dose of the day on Treatment Days 8, 15, 22, and in the morning of Day 29.

On Day 29, after the 24-hour blood draws in the oral groups (Treatments “A”, and “B”) and after the PK/PD blood draws in the Treatment “D” and the IM injection group (Treatment “C”), physical, gynecological, and safety laboratory evaluations will be performed.

Note: Throughout the text, Treatment Day 29 may be used interchangeably with Postdosing Day 1.

Four follow-up visits will be scheduled at 7, 14, 21 and 28 days after the last dose (Treatments “A”, “B”, and “D”) or the last day of the 28-day dosing cycle (Treatment “C”). During each follow-up visit, blood samples will be drawn to assess leuprolide (via a single blood draw) and LH, FSH, E2, and progesterone concentrations. During each follow-up visit, subjects will be asked about onset (or absence) of menstrual period.

Safety laboratory evaluations will also be performed during the 28-day postdosing visit. The 28-day postdosing visit will be considered the Final Study Visit. In addition, to the PK/PD and safety laboratory assessments, ECG, physical and gynecological examinations will also be performed.

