## **8. ELIGIBILITY CRITERIA**

### **8.1 Inclusion Criteria**

Subjects enrolled in this study will be members of the community at large. The recruitment advertisements may use various media types (*eg*, radio, newspaper). Subjects must meet all of the following criteria to be included in the study:

- 1) Healthy premenopausal female volunteers, aged 18 to 49 years
- 2) BMI  $\geq 18$  and  $\leq 32$  kg/m^2, and weight  $\geq 110$  lb ( $\approx 50$  kg).
- 3) Regular menstrual cycles with a usual length ranging from 21 days to 35 days. If subject has recently used hormonal birth control, historical data prior to use will be used to determine qualification and must also meet this criterion.

- 4) If of childbearing potential and sexually active with a risk of pregnancy, willing to use one of the following acceptable methods of contraception throughout the study and for at least 30 days after the last drug administration:
  - a) intrauterine contraceptive device without hormone release system placed at least 4 weeks prior to the first study drug administration with simultaneous use of condom for the male partner
  - b) simultaneous use of diaphragm with intravaginally applied spermicide and condom for the male partner starting at least 14 days prior to drug administration.
  - c) sterile male partner (vasectomized for at least 6 months)
  - d) Note: Surgically sterile subjects who have had a tubal ligation are considered of non-childbearing potential and are not required to use contraception
- 5) Willing to refrain from excessive use of alcohol during the entire study and willing to refrain from use of alcohol 24 hours prior to any PK blood draw taken during the study
- 6) Willing to refrain from use of prescription medications, over-the-counter medications and natural health products during the entire study
- 7) Willing and capable to give informed consent to participate in study

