## **13. Handling of Missing Data**

Only observed data will be used in the data analysis except for concentration values BLQ and samples with no reportable value occurring prior to dosing (on Day 1 only) as described in section 10.1. No attempt will be made to impute (i.e., extrapolate or interpolate) estimates for missing data.

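### SAP 11.2 misclassifies menstrual onset at both edges of the 28-day postdosing window, and for a suppressed woman the window may close before her next period is due

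*SAP*

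**What the plan says.** SAP 11.2 gives the definition: "The onset of menstrual period is defined as at least three consecutive bleeding/spotting days during the 28-day postdosing period". It is reported as a simple proportion: "The subject incidence of the onset of menstrual period after completion of therapy will be reported for each treatment group".

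Four other provisions bear on it.

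- The diary card in Protocol Appendix F (Part 2) has columns for Postdosing Days 1 to 28 and no more. On numbering, the Protocol synopsis says: "Throughout the text, Treatment Day 29 may be used interchangeably with Postdosing Day 1".
- Protocol 8.1 admits women with "Regular menstrual cycles with a usual length ranging from 21 days to 35 days".
- On incomplete data, SAP 13 says: "No attempt will be made to impute (i.e., extrapolate or interpolate) estimates for missing data". For categorical summaries SAP 11.2 adds: "In addition, the number of patients with missing values will be displayed".
- Protocol 7.1 provides a second source: "During each follow-up visit, subjects will be asked about onset (or absence) of menstrual period". The SAP definition does not use that answer.

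No rule covers a run cut off by the end of the diary, a bleed already under way on Postdosing Day 1, or a woman who leaves before Day 28.

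**The concern.** The definition requires the whole three-day run to lie inside a fixed window, and does not say that the run must begin there. This has opposite effects at the two ends: true onsets in the last two days are lost, and bleeds carried over from dosing are gained.

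The window is also short against the eligible cycle lengths. A woman who was suppressed and restarts a cycle when dosing ends is due her next period about one cycle later, which can be after the last day that counts. A woman whose cycle was never disturbed nearly always has a period due inside the window. A low incidence may therefore reflect effective suppression with normal recovery, and a high incidence may reflect absence of suppression.

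Protocol Section 5 presents the ability to stop an oral product at once as a possible advantage over the injection. A table labelled as onset of menses after therapy, by arm, invites a reading about reversibility that it cannot carry alone.

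**Working it through.** The plan states no rate or sample size for this endpoint, so there is no figure to reproduce. The check is by counting.

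**1. Latest qualifying start.** With a 28-day window and a 3-day run, the last start is 28 - 3 + 1 = Day 26. A start on Day 27 leaves two diary days, and a start on Day 28 leaves one.

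**2. Early edge.** A bleed that starts on the last dosing day (Day 0) and lasts four days covers Days 1, 2 and 3. It meets the definition although it began on treatment.

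**3. Suppressed woman, immediate restart.** Let cycle day 1 fall on postdosing day c and let the usual length be L, a whole number from 21 to 35 (15 values, Protocol 8.1). Menses are due on day c + L and are missed if c + L > 26.

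- c = 0 (last-dose day): L = 27 to 35 are missed, 9/15 = 60%.
- c = 1 (Postdosing Day 1): L = 26 to 35 are missed, 10/15 = 67%.

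At c = 0, two of the nine lengths (27 and 28 days) fall due on Days 27-28 and are lost through the definition: 2/15 = 13%. The other seven (29 to 35 days) fall due after the diary ends: 7/15 = 47%. If restart is delayed by 3 days, 12 of 15 are missed at c = 0 and 13 of 15 at c = 1. With a 7-day delay all 15 are missed.

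**4. From lengths to women.** The documents give a range but no distribution. Assuming a normal distribution in whole days, truncated to 21-35, with SD 2 to 4, the share of women missed (covering c = 0 and c = 1) is:

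| Assumed mean length (days) | Share missed |
|---|---|
| 25 | 23-52% |
| 26 | 40-60% |
| 27 | 57-77% |
| 28 | 66-89% |
| 29 | 73-96% |
| 30 | 80-99% |

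A majority is missed only if the median length exceeds about 25-26 days.

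**5. Undisturbed woman, for contrast.** If dosing starts on cycle day s and the drug has no effect, menses fall on postdosing days kL - s - 26 for k = 0, 1, 2 and so on. Using the start days in Protocol Appendix G for A, B and C (15 lengths x 15 start days = 225), 219 combinations (97%) have a start on Days 1-26. Using 5 to 9 days before expected menses for D (15 x 5 = 75), all 75 do. In each of the six A/B/C exceptions a bleed starts on Day 0 or Day -1, so a long enough bleed would enter by the route in step 2.

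**6. Comparator label (Protocol Appendix D).** The label reports: "In the first, second and third post-treatment months, normal menstrual cycles resumed in 7%, 71% and 95% of patients, respectively". It also describes stable drug levels for about four to five weeks, past Treatment Day 28. If 7% applied to the five women in Treatment C, the chance of seeing no onset would be 0.93^5 = 0.70. This is indicative only, because the label figure is for resumption of normal cycles in endometriosis patients after six monthly injections, not for three days of bleeding or spotting in healthy volunteers after one.

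**The case against.** **The endpoint is minor.** Return of menses appears in no study objective (SAP 2), the primary PD metric is E2 suppression (SAP 11.1), and the SAP plans no inferential analysis (Section 8). This stands and limits the priority.

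**Hormones already tell recovery from non-recovery.** SAP 11.2 summarises LH, FSH, E2 and progesterone at postdosing Days 7, 14, 21 and 28, and time to return to baseline levels may be estimated. A reader might infer that the report could not separate a recovering woman from one who is not recovering. That goes too far. The menses table alone cannot do it, but the hormone data partly can, which is why the two should be read together.

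**Few women are affected.** Protocol Section 5 reports that A and B fell well short of depot suppression, so many of those women may simply have continued their own cycles. The problem in step 3 concerns mainly Treatment C (five women) and an unknown part of D (at most twelve). This stands.

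**Early leavers.** A reader might infer that they are scored as no onset. No section says so. SAP 11.2 displays missing counts and SAP 13 uses observed data only. Of the 23 women first enrolled, only one did not complete (SAP 3.1). The gap is an unstated classification and denominator.

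**Time-to-event methods add little.** If every woman completes the diary, the Kaplan-Meier onset estimate at Day 28 equals the crude incidence and cannot recover onsets that occur later. This stands. The gain is in showing when onsets occurred, treating early leavers explicitly, and labelling the remainder as not yet observed.

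**Counting open runs relaxes the definition.** One day of spotting on Day 28 is not a period. This also stands, and is the reason to show such runs as a category of their own.

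**Conclusion.** The concern holds in a limited form. Three things follow directly from the text: the latest qualifying start is Day 26, a period starting on Day 27 or 28 is classified as no onset, and a bleed carried over from dosing can be classified as a post-therapy onset.

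That the window is short for suppressed women is exact as a count of eligible lengths: 9 or 10 of 15 under immediate restart. As a share of women it is an assumption, 23-99% over the distributions tried. The stronger claim that most women with a full cycle to complete cannot meet the definition is not supported. The documents give no cycle-length distribution, spotting counts, no ovulatory menses is required, and a bleed spanning Day 1 can qualify. Most of the shortfall (7 of the 9 lengths) comes from the length of follow-up and not from the SAP wording, so rewording can label it but cannot remove it. Priority is low to moderate.

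**What to change.** In SAP 11.2:

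1. Date onset by the first day of the run, and do not count a run that began before Postdosing Day 1 as a new onset.
2. Report runs that start on Day 27 or 28 and are still open when the diary ends as a separate category. Give the incidence with and without them, using the Day 28 visit answer on menstrual onset as support.
3. Add time from end of dosing to onset, censored at the last completed diary day, with early leavers shown as censored and not as no onset.
4. State beside the table that no onset by Day 28 is not evidence of failed recovery and is to be read with the postdosing hormone levels.

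The diary dates and visit answers are already collected, so no visit or sample changes. The cost is SAP wording and one extra descriptive table. The drawback is that some open runs may prove shorter than three days, which showing both incidences makes visible.
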